 - o. An increase in AST or ALT $> 3 \times$ ULN should be followed by repeat testing within 72 hours of receiving results to confirm the abnormality and determine whether AST or ALT is increasing or decreasing.
 - p. For women of childbearing potential, the first pregnancy test at Screening is a serum β -hCG test that is evaluated by a central laboratory. All subsequent pregnancy testing will be performed using a urine dipstick pregnancy test. Home urine pregnancy test kits may be provided to the participant for any virtual/hybrid visit or to perform a monthly pregnancy test at home during non-visit months, if permitted by local regulations. Participants will confirm the performance of a monthly pregnancy test in the eDiary, if performed at home, and provide the results to the study site. Any positive urine pregnancy test will be confirmed with a serum β -hCG test by a central laboratory.
 - q. Coagulation panel to be performed at an unscheduled visit in case of elevated ALT/AST.
 - r. Complete physical examination at Screening, brief physical examinations during the study, and complete physical examination at Visit 12/ET (see [Table 2](#)). A complete physical examination will include evaluation of heart, lung, head and neck, abdomen, neurological function, skin, and extremities. An interim (or brief) physical examination will include areas with previously noted abnormalities and/or that are associated with any new complaints from the participant.
 - s. Pulmonary function includes assessment of FEV1 and FVC. If the pulmonary function test results are not within normal range, the results should be verified by a pulmonologist, and potential confounding factors identified. If the participant has a decline in pulmonary function test values, the participant should be evaluated by a pulmonologist. If values (FEV1 and/or FVC) decline below 50% of the predicted values, treatment should be discontinued with follow-up evaluation initiated as appropriate. At sites where available, DLCO measurements will also be performed.

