6.6 Guidance for Hepatic Monitoring

An increase in AST or ALT $> 3 \times$ ULN should be followed by repeat testing within 72 hours of receiving results to confirm the abnormality and determine whether AST or ALT is increasing or decreasing.

Discontinuation of study treatment for abnormal liver function should be considered by the Investigator when a participant meets one of the conditions outlined below or if the Investigator believes that it is in best interest of the participant. See also [Section 7.1](#) for more information.

- ALT or AST $> 8 \times$ ULN
- ALT or AST $> 5 \times$ ULN for > 2 weeks
- ALT or AST $> 3 \times$ ULN and total bilirubin $> 2 \times$ ULN or international normalized ratio (INR) > 1.5
- ALT or AST $> 3 \times$ ULN with the appearance of fatigue, nausea, vomiting, right upper quadrant pain or tenderness, fever, rash, and/or eosinophilia ($> 5\%$)

All events of ALT or AST $> 3 \times$ ULN and total bilirubin $> 2 \times$ ULN ($> 35\%$ direct bilirubin), or ALT or AST $> 3 \times$ ULN and INR > 1.5 , if INR measured, which may indicate severe liver injury (possible Hy's Law), must be reported as an SAE. See [Section 8.5](#) for follow-up and reporting of SAEs.

Because transient fluctuations of ALT or AST are common, and progression to severe drug-induced liver injury or acute liver failure is uncommon, automatic discontinuation of study treatment upon finding a greater than $3 \times$ ULN elevation of ALT or AST may be unnecessary.

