7.0 DISCONTINUATION OF STUDY TREATMENT AND PARTICIPANT DISCONTINUATION/WITHDRAWAL

7.1 Discontinuation of Study Treatment

A participant's study treatment may be discontinued for any of the following reasons:

- Worsening of disease, defined as:
 - Induction Treatment Period:
 - Based on Investigator's decision, administration of prohibited medication for treatment of UC during the Induction Period
 - LTE Treatment Period:
 - Based on Investigator's decision, administration of prohibited medication for treatment of UC during the LTE Treatment Period
 - OLE Treatment Period:
 - Participant fails to achieve symptomatic response by OLE Week 13 (among participants who had no clinical response at the end of the Induction Period)
 - Participant experiences loss of response
- AE, see [Appendix 4](#):
 - A participant may be discontinued from the study drug if, in the judgment of the Investigator, the participant develops an AE such as an intercurrent illness or complication that is not consistent with the protocol requirements or that, in any way, justifies withdrawal from the study.
- Discontinuation of study treatment for abnormal liver function should be considered by the Investigator when a participant meets one of the conditions outlined below or if the Investigator believes that it is in best interest of the participant.
 - ALT or AST $> 8 \times$ ULN
 - ALT or AST $> 5 \times$ ULN for > 2 weeks
 - ALT or AST $> 3 \times$ ULN and total bilirubin $> 2 \times$ ULN or INR > 1.5
 - ALT or AST $> 3 \times$ ULN with the appearance of fatigue, nausea, vomiting, right upper quadrant pain or tenderness, fever, rash, and/or eosinophilia ($> 5\%$).
- Other, non-AE

A participant's study treatment must be discontinued temporarily (treatment interruption) for any of the following reasons:

- New onset QTcF interval prolongation
 - If an ECG shows a new onset QTcF interval > 450 msec in men and > 470 msec in women during the treatment period, a repeated ECG is required. If this abnormal finding is

confirmed, study treatment must be temporarily discontinued. Reinitiation of study treatment can be considered per criteria described in [Section 8.4.3](#).

- Lymphopenia (ie, severe decrease in ALC)

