- b) Details of liver chemistry stopping criteria and required actions and follow-up assessments after liver stopping or monitoring event are given in [Section 6.6](#). An increase in AST or ALT $> 3 \times$ ULN should be followed by repeat testing within 72 hours of receiving results to confirm the abnormality and determine whether AST or ALT is increasing or decreasing. All events of ALT or AST $> 3 \times$ ULN and total bilirubin $> 2 \times$ ULN ($> 35\%$ direct bilirubin), or ALT or AST $> 3 \times$ ULN and INR > 1.5 , if INR measured, which may indicate severe liver injury (possible Hy's Law), must be reported as an SAE.
- c) eGFR will be calculated each time the serum creatinine is tested.

[REDACTED]

Appendix 4 Adverse Events: Definitions and Procedures for Recording, Evaluating, Follow-Up, and Reporting

See [Section 8.5](#) for additional information regarding AEs and SAEs.

Definition of AE

AE Definition
 
 • An AE is any untoward medical occurrence in a participant, temporally associated with the use of study treatment, whether or not considered related to the study treatment. • NOTE: An AE can therefore be any unfavorable and unintended sign (including an abnormal laboratory finding), symptom, or disease (new or exacerbated) temporally associated with the use of study treatment.

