17.2.2 Lab Values and Normal Ranges

[REDACTED] For purposes of data analysis, ADAM.ADLB (and any other ADaM datasets with laboratory data) will put a limited number of central lab values and normal ranges on a common footing, with [REDACTED] normal ranges serving as the reference ranges. Local lab data will not be transformed in this way. The analytes subject to normalization are absolute lymphocyte count (ALC), absolute neutrophil count (ANC), and high-specificity c-reactive protein (CRP).

³ <https://reference.medscape.com/calculator/251/egfr-using-ckd-epi-2021-update>

[REDACTED] data for ALC, ANC, and CRP will be mapped to [REDACTED] normal ranges. In some cases age and/or sex may need to be taken into account for a given central laboratory and analyte.

To match the manner in which the two central laboratories handle participant Age, the following rules will be applied during the analyte normalization process:

- [REDACTED] participant Age at collection during Screening / Baseline will be incremented by +1 every 30 Jun
- [REDACTED] participant Age at collection during Screening / Baseline will be incremented by +1 every 01 Jan

These Age rules are specific to the analyte normalization process.

The analyte mapping will be done according to the following formulas and the notation in these formulas suppresses both age and sex demographic characteristics for simplicity:

[REDACTED]

[REDACTED]

[REDACTED]

[REDACTED]

[REDACTED]

[REDACTED]

[REDACTED]

[REDACTED]

[REDACTED]

[REDACTED]

[REDACTED]

[REDACTED]

[REDACTED]

[REDACTED]

[REDACTED]

[REDACTED]

[REDACTED]

[REDACTED]

[REDACTED]

[REDACTED]

[REDACTED]

[REDACTED]

[REDACTED]

[REDACTED]

[REDACTED]

[REDACTED]

[REDACTED]

Transformation

Let X_{OBS} = observed lab value

Let X_{REF} = transformed lab value

- [REDACTED]
[REDACTED]
[REDACTED]
[REDACTED]
[REDACTED]
[REDACTED]
[REDACTED]
[REDACTED]
[REDACTED]
[REDACTED]
- [REDACTED]
[REDACTED]
[REDACTED]
[REDACTED]
[REDACTED]

Flag values for individual lab assays (e.g., ‘low’ vs ‘normal’ vs ‘high’, or ‘Abnormal, clinically significant’ vs ‘Abnormal, not clinically significant’ vs ‘Normal’) will not be altered as a result of mapping lab values and normal ranges. These flag values, as determined by central laboratory, will be used in listings and tables. Composite events relying on multiple cutoff values, such as cases of potential drug-induced liver injury, will also be determined using original central lab values and normal ranges.

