 - Shift tables for the change in CTCAE toxicity grades (with separate parts for decreased and increased grades and Grade = 0 for normal results) from baseline to every post-baseline visit and worse post-baseline visit in Induction Treatment Period

- The number of participants in a particular treatment group having both baseline and post-baseline results available will be used as the denominator.
- Listings
 - Listings will present data in both conventional (CN) and international system (SI) units
 - Hematology, serum chemistry, urinalysis, coagulation data, and pregnancy test data will be listed and these listings will include both central laboratory and local laboratory data.
 - Laboratory values outside normal limits will be identified in the participant data listings with appropriate flags (e.g., ‘Normal’ vs ‘Low’ vs ‘High’ or ‘Abnormal, clinically significant’ vs ‘Abnormal, not clinically significant’ vs ‘Normal’). Abnormal lab values and CTCAE grades over time will be summarized by number and percentage.

Additionally, the number and percentage of participants meeting the following criteria will be presented by treatment group and visit:

- Elevated ALT or AST levels ($>3 \times \text{ULN}$ and total bilirubin $> 2 \times \text{ULN}$ or international normalized ratio (INR) > 1.5 ; $>5 \times \text{ULN}$ for > 2 weeks and $>8 \times \text{ULN}$).
- ALT or AST $> 8 \times \text{ULN}$
- ALT or AST $> 5 \times \text{ULN}$
- ALT or AST $> 3 \times \text{ULN}$
- ALT or AST $> 3 \times \text{ULN}$ and total bilirubin $> 2 \times \text{ULN}$
- ALT or AST $> 3 \times \text{ULN}$ and INR $> 1.5 \times \text{ULN}$

The denominator will be the number of participants in treatment group with non-missing data at specified visit.

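### The last liver row in SAP 17.2.3 sets INR at 1.5 × ULN, where the protocol and the first bullet of the same list use an absolute INR above 1.5

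*SAP*

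**What the plan says.** **SAP 17.2.3 (Summaries)** ends with six liver criteria, to be tabulated as numbers and percentages by treatment group and visit. The sixth is "ALT or AST $> 3 \times \text{ULN}$ and INR $> 1.5 \times \text{ULN". The first is a compound entry covering the bilirubin, INR, prolonged 5 × ULN and 8 × ULN conditions. In it the INR cut-off is a plain 1.5, with no multiple of ULN.

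**SAP 17.2.2** says that composite events "such as cases of potential drug-induced liver injury, will also be determined using original central lab values and normal ranges".

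**Protocol 6.6** lists conditions under which the investigator should consider stopping treatment. One is ALT or AST above 3 × ULN with bilirubin above 2 × ULN "or international normalized ratio (INR) > 1.5". The same section says that ALT or AST above 3 × ULN with INR above 1.5, as a possible Hy's Law event, "must be reported as an SAE".

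**Protocol 7.1** repeats the discontinuation condition: "ALT or AST $> 3 \times$ ULN and total bilirubin $> 2 \times$ ULN or INR > 1.5".

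**Protocol Appendix 3**, footnote b to the laboratory table, repeats the SAE rule with an INR above 1.5, "if INR measured, which may indicate severe liver injury".

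**SAP 18** declares two departures from the protocol: the numbering of screening days and separate modelling of fecal calprotectin by laboratory. Neither concerns INR.

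**The concern.** One SAP list defines two INR cut-offs for what appears to be the same concept. A programmer following the text literally would code both. The row that isolates transaminases plus INR is the natural place to look for the INR side of the protocol's possible Hy's Law criterion, and it carries the cut-off that the protocol does not use.

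The ALT/AST and bilirubin multiples in the list all occur in Protocol 6.6; the INR multiple occurs nowhere else in either document. It looks as if the ULN wording was carried down from the rows above, although the documents do not say so.

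What is at stake is the accuracy of one by-arm safety count. It matters because INR is part of how the trial follows up raised transaminases: Table 1 of the protocol, footnote q, says "Coagulation panel to be performed at an unscheduled visit in case of elevated ALT/AST".

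**Working it through.** The plan states no figure to reproduce. The check compares the texts and then does one multiplication.

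**Step 1. Every INR cut-off in a liver criterion**

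| Place | Purpose | INR cut-off |
|---|---|---|
| Protocol 6.6 | Consider discontinuation | > 1.5 |
| Protocol 6.6 | Mandatory SAE report (possible Hy's Law) | > 1.5 |
| Protocol 7.1 | Consider discontinuation | > 1.5 |
| Protocol Appendix 3, footnote b | Mandatory SAE report | > 1.5 |
| SAP 17.2.3, first liver bullet | By-visit count, compound | > 1.5 |
| SAP 17.2.3, last liver bullet | By-visit count, transaminase plus INR only | > 1.5 × ULN |

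Five of the six agree; the last SAP bullet is the exception.

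**Step 2. What the relative cut-off becomes**

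Cut-off = 1.5 × (INR ULN). The documents give no INR ULN, so the values below are assumptions. The width of the missed band is the cut-off minus 1.5.

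| Assumed INR ULN | Row's cut-off | INR values above 1.5 that the row omits |
|---|---|---|
| 1.0 | 1.5 × 1.0 = 1.50 | none |
| 1.1 | 1.5 × 1.1 = 1.65 | above 1.5 up to 1.65 (width 0.15) |
| 1.2 | 1.5 × 1.2 = 1.80 | above 1.5 up to 1.80 (width 0.30) |
| 1.3 | 1.5 × 1.3 = 1.95 | above 1.5 up to 1.95 (width 0.45) |

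The two rules coincide only at a ULN of exactly 1.0. Above that, the SAP row is the stricter one.

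**Step 3. A worked case**

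Take a participant with ALT 4 × ULN, normal bilirubin and INR 1.6.

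- Protocol 6.6 SAE rule: 4 > 3 and 1.6 > 1.5, so it is met.
- SAP first liver bullet: counted, on the same comparison.
- SAP ALT or AST > 3 × ULN row: counted.
- SAP bilirubin row: not counted, because bilirubin is normal.
- SAP INR row: not counted once 1.5 × ULN reaches 1.6, that is at ULN ≥ 1.6 / 1.5 = 1.067.

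The case stays in the output, but at a ULN of about 1.07 or more it is missing from the row whose description fits it best.

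**The case against.** The strongest reply is that the protocol's criterion is already in the plan. The first bullet carries the absolute INR cut-off, and the worked case counts there. Coagulation data are listed from central and local laboratories, and SAE reporting is governed by the protocol whatever the SAP tabulates. All of this stands, and it limits the point to one row. It does not remove the conflict. The first bullet mixes several conditions, and SAP 19 leaves its layout to the mock tables, so in the SAP text the last bullet is the only row that isolates transaminases plus INR.

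A second reply is that the later bullets are general laboratory thresholds and not copies of protocol criteria. The 5 × ULN row drops the two-week duration, the bilirubin row omits the direct-bilirubin qualifier, and the INR row is not labelled as Hy's Law. That is a fair reading of the list, but it supplies no reason for a relative INR cut-off.

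Four stronger readings are tempting, and the documents do not support them:

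- **That the row could otherwise be reconciled with the SAE tables.** SAP 17.1.2 builds those tables by system organ class, preferred term, relatedness and grade. They would not map directly onto a by-visit laboratory count even after the correction.
- **That the cut-off differs between participants because there are two laboratories.** SAP 17.2.2 does refer to how "the two central laboratories handle participant Age", but in connection with normalizing lymphocytes, neutrophils and CRP. Nothing shows that the laboratories have different INR limits, and the protocol's own composite already depends on each laboratory's ALT, AST and bilirubin limits.
- **That a missed case can be expressed as a share of the 63 participants planned per arm.** SAP 17.2.3 uses as denominator those with data at the visit concerned, and that number cannot be derived from the documents. Unscheduled results are also windowed under SAP 9.6, so an unscheduled INR may not reach the by-visit row under either cut-off.
- **That this is an undeclared departure from a planned protocol analysis.** Protocol 9.4.3 prescribes no INR table. The mismatch is with a safety criterion and within one SAP list.

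**Conclusion.** The inconsistency is real and certain on the text. If the SAP is followed literally, the transaminase-plus-INR row is stricter than the protocol's possible Hy's Law INR criterion whenever the INR ULN exceeds 1.0, and it can then omit participants who meet that criterion. The size rests on the INR ULN, which the documents do not give: over the assumed range of 1.0 to 1.3 the cut-off runs from 1.50 to 1.95. How many participants would fall in the gap cannot be estimated and may be none.

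The point is minor. The table is descriptive, affected cases remain visible elsewhere, and no efficacy result, alpha allocation, dosing decision or SAE obligation changes.

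**What to change.** In SAP 17.2.3, change the last liver bullet to ALT or AST > 3 × ULN and INR > 1.5, by deleting the ULN multiplier after the INR value. Make the same change to the table label and the programming specification. The row then agrees with Protocol 6.6, 7.1 and Appendix 3 and with the first bullet of its own list.

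The cost is one edited bullet and its label. It requires no new data collection and changes no other analysis. If a relative INR cut-off is in fact wanted, keep it as an additional row with its reason stated, beside the absolute one.

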17.3 Vital Signs

Similar to laboratory data analysis, three sets of vital signs summaries will be prepared: for Induction Treatment Period, LTE and OLE Treatment Periods. Safety Set will be used for induction treatment summaries and Safety-ET Set for LTE/OLE summaries.

Vital signs include data on pulse rate (bpm), systolic/diastolic blood pressure (mmHg), respiratory rate (breaths/min), temperature ($^{\circ}\text{C}$), weight (kg) and height (cm). Descriptive statistics will be provided for observed values, change from baseline, and percent change from baseline to post-baseline time points for every parameter. Visit windowing will be used to associate vital sign data with study visits – see [Section 9.6 Table 3](#).

A listing of vital signs data will be presented.

17.4 Physical Examination

A listing will be provided for physical examination findings including description of any abnormalities.

17.5 Electrocardiogram (ECG)

Similar to laboratory data analysis, three sets of ECG summaries will be prepared: for Induction Treatment Period (Safety Set), LTE and OLE Treatment Periods (Safety ET Set).

17.5.1 Twelve-Lead ECG

ECG data will be presented by treatment group for each study period (Induction, LTE, OLE) and overall.

The 12-lead ECG data will include heart rate (bpm), RR (msec), PR (msec), QRS (msec), QT (msec) and QTcF (msec) intervals. Absolute values and changes from baseline to post-baseline time points will be summarized using descriptive statistics for quantitative variables. Shift tables from baseline ('Normal', 'Abnormal, not clinically significant' and 'Abnormal, clinically significant') to each visit will be provided. ECG data will be read locally as well as centrally. Only central ECG data will be used for summaries, all available ECG data from local and central readers will be listed. Actual results will not be reconciled. In case of several assessment within timepoint, the earlier assessment will be used for the analysis.

The following incidences will be summarized by number and percentage at every post-baseline visit:

- QT interval
 - ≥ 500 msec
 - Change from baseline $> +30$ msec
 - Change from baseline $> +60$ msec
- QTcF interval
 - ≥ 450 msec (male) or ≥ 470 msec (female)
 - Change from baseline $> +30$ msec
 - Change from baseline $> +60$ msec
- PR interval
 - PR > 200 msec
 - PR > 230 msec
- HR
 - < 40 beats/min (bpm)

- < 50 bpm
- > 110
- Change from baseline < -10 bpm
- AV Block
 - First-degree AV Block
 - Second-degree AV Block Type 1
 - Second-degree AV Block Type 2
 - Third-degree AV Block

The denominator will be the number of participants in treatment group with non-missing results at the specified visit.

17.5.2 Holter ECG monitoring

On Day 1 of Induction Treatment Period and OLE Day 1 continuous Holter ECG monitoring will be performed for at least 1 hour predose and at least 24 hours postdose.

Overall interpretation ('Normal', 'Abnormal', 'Not Evaluable') will be summarized by number and percentage. Denominator will be the number of participants available at specified visit in treatment group.

Parameters of interest will be listed.

17.6 Optical Coherence Tomography

Four summaries will be prepared: for Induction Treatment Period (Safety Set), LTE, OLE, and overall, using the Safety and Safety-ET sets.

Shift tables from baseline ('Normal', 'Abnormal, not clinically significant' and 'Abnormal, clinically significant') to each visit will be provided. Denominator will be the number of participants in treatment group with non-missing results at specified visit.

17.7 Pulmonary Function Test

Similar to laboratory data analysis, four sets of summaries will be prepared: for Induction Treatment Period (Safety Set), LTE, OLE, and overall, using the Safety and Safety-ET sets.

The pulmonary function test data will include the following parameters: Forced Expiratory Volume (FEV1) (L), Predicted FEV1 (L), Percentage of predicted FEV1 (%), Forced Vital Capacity (FVC) (L), FVC (%), Peak Expiratory Flow Rate (PEFR) (L/sec), Forced Expiratory Flow (FEF) (L/sec), Total Lung Capacity (L), Percentage of Total Lung Capacity (%), Predicted Total Lung Capacity (L), DLCO, predicted DLCO, percentage of predicted DLCO.

Absolute values and changes from baseline to post-baseline time points will be summarized using descriptive statistics for quantitative variables. Abnormal findings and incidences of FEV1, FVC, and/or FEV1/FVC ratio will be summarized by number and percentage. Denominators will be the number of participants in treatment group with non-missing results at specified visit.

All pulmonary function test data will be listed. The following criteria will be used to define abnormal findings and incidences:

- Decrease from baseline > 20% in FEV1 (absolute value)
- Decrease from baseline > 20% in FVC (absolute value)
- Decrease from baseline > 20% in DLCO (absolute value)
- Decrease from baseline in % predicted FEV1 > 20%
- Decrease from baseline in % predicted FVC > 20%
- Decrease from baseline in % predicted DLCO > 20%
- % Predicted FEV1 < 50%
- % Predicted FVC < 50%
- % Predicted FEV1/FVC ratio < 50%

